##### Side Effects

As in our past varenicline trials (Patterson et al., 2009; [name] et al., 2011), a checklist and open-ended questions will assess the frequency and severity of varenicline-related side effects at all time-points after the Intake Session over the course of the 24-week study, before and after medication initiation. These assessments monitor participant safety and dose reductions or suspension can occur. Side effects will be a study outcome and can be a covariate in the analysis as the overall frequency and/or as the presence (ever) of specific side effects. This measure includes psychiatric events (e.g., depressed mood, suicidal ideation; Kuehn, 2008) and cardiovascular side effects.

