## **2. Statistical Analysis**

### **Power**

Power is provided for the primary aims since the exploratory aim is hypothesis generating. Power calculations were all approximated as t- or z-tests (2-sided,  $\alpha = .05$ ), and conducted using PASS Software (Power and Sample Size, NCSS Software, Kaysville, UT).

Aim 1: The primary analysis is a comparison in week 12 and 24 cotinine-confirmed 7-day point prevalence quit rates between placebo and varenicline. For the week 12 comparison, we based our sample size selection on the expectation that quit rates in the placebo and varenicline arms would approximate those reported in past varenicline trials with the general population of smokers (i.e., placebo = 21.2%; varenicline = 50.3%; Gonzales et al., 2006). With a sample of 310, we have >90% power to detect a significant effect between our treatment arm. Notably, we have 80% to detect a difference in week 12 quit rates if the difference between treatment arms is as small as 15%, not 29% as found in Gonzales et al. (2006), since the effect for varenicline may be smaller in this sub-group of smokers. For the week 24 comparison, we based our sample size on the expectation that the quit rate in the placebo arm would be 14.5%, vs. 33.5% for varenicline (Gonzales et al., 2006). In this case, we have 85% power to detect a significant difference between treatment arms. However, we have 80% power to detect a difference between treatment arms if the treatment arm difference is only 15%, not the 19% reported in Gonzales et al. (2006), since the effect for varenicline may be smaller in this sub-group of smokers. Even though it may appear that we are over-powered for Aim 1, we require the proposed sample to conduct the non-inferiority analyses for Aim 2.

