Aim 2: The analyses are a comparison in week 12 and 24 differences in QOL and severe side effects. For QOL, the overall scale mean among HIV/AIDS patients is 58.3 (SD = 24.5, Range 14-100; Holmes & Shea, 1998). We have 80% power to detect a mean difference of 7.8 at any time-point between the treatment arms with the proposed sample of 310. For side effects, the analyses will involve a test of non-inferiority since we cannot use standard statistical tests and conclude that a non-significant comparison shows that the drug is safe (i.e., "the absence of evidence is not evidence of absence"). In our past study with varenicline, 61% of participants on varenicline reported no severe side effects, vs. 76% of participants on placebo, a 15% difference (Patterson et al., 2009). With the present sample size, we will have 80% power to detect similar equivalence between treatment arms in terms of the frequency of severe side effects over the course of the 12-week treatment, given that side effects are actually non-significantly different across the treatment arms.

Aim 3: The analyses will assess changes in affect and cognitive function as mediators of treatment arm effects at week 12 and 24. These measures are continuous difference scores. Our sample of 310 is well above the minimum sample of 200 recommended for models of this size (Haduk, 1987; Boosma & Gabrielli, 1985). The mediation hypothesis will examine the proportion of treatment effect explained (Lin et al., 1997; Vittinghoff et al., 2009), and will test each mediation hypothesis with a z-score generated using the delta method. Our sample of 310 gives us 80% power to observe small effects in a 1-sample test ( $\delta=0.20$ ) when testing at  $\alpha=0.05$ . There are four proposed mediating pathways (2 measures of affect and cognition, respectively) between treatment and outcome, so our type-1 error will be corrected to 0.0125. Our sample of 310 gives us 80% power to detect small to medium effects ( $\delta=0.19$ ) for changes in the proposed mediators, which we have seen in previous trials (Patterson et al., 2009; [name] et al., 2010a).

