### **Data Analysis**

[name] will oversee analyses which will be conducted using Stata, SAS, or R-Language software. Preliminary analyses will assess sample characteristics by treatment with chi-square or logistic regression (e.g., gender, dependence, depression). These variables will also be examined for their relationship to completion of outcome assessments. Variables related to treatment arm or completion of follow-ups will be included as covariates in analyses of study aims. Compliance measures will be evaluated across treatment arms, and controlled for in primary analyses. We will examine the correlation between self-report and pill count data and week 3 and 12 varenicline levels. Although we will use intent-to-treat as the primary method for

[figure not shown]
evaluating study aims, we will conduct a completers only analysis of study aims and examine study aims with participants lost to follow-up due to death excluded as done previously ([name] et al., 2003).

**Missing Data:** We will examine if the rate of missing data, primarily our smoking cessation outcome data, is related to a range of potential variables, including treatment arm allocation and HIV/AIDS-related, demographic, and smoking-related variables. Standard statistical methods will be used to identify possible correlates of missing data such as chi-square and regression. Variables found to be associated with the rate of missing data ( $p < .05$ ) will be included as covariates in the analyses of aims. In the event of items missing at random on measures, items will be imputed prior to calculating final scores using conditional means, estimated with an iterated version of Buck's method (Gleason & Staelin, 1975). Dropout and missed sessions present a more serious issue. The best way to deal with this is to avoid the problem in the first place by keeping subjects connected to the trial and motivated to complete measures. In our clinical trials, compliance and retention rates were >80% thanks to our close monitoring of participants and use of incentives to offset travel costs ([name] et al., 2008). Primary analyses will assume that all subjects for whom smoking outcome data are unavailable are smokers (intent-to-treat). This assumption, which is conventional in smoking cessation research, can attenuate the differences between study groups in quit rates. Thus, we will also conduct a "completers-only" analysis.

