**Aim 2: Assess effects of varenicline therapy on QOL and side effects.** Repeated-measures MANOVA will examine differences across treatment arms in QOL (total scale score and subscale scores) over the trial. Participant covariates will be included, such as medical treatment history. In addition, we will compare treatment arms in terms of the frequency of severe side effects (*individual, including cardiovascular side effects, and total*). Using logistic regression, we will test against the lower boundary on percent reporting only mild-moderate (i.e., < severe) side effects. The hypothesis test for equivalence is a test of whether the OR is out of the prescribed range for the difference between the treatment arms. This approach provides a more valid test of the potential safety of varenicline for individuals with HIV/AIDS vs. a simple comparison of mean responses on a side effects measure. *We will also examine if participants on tenofovir (vs. other HAART) experience a greater frequency or more severe varenicline side effects by including type of HAART as a covariate in these analyses and, if so, we can explore if this relationship is mediated by varenicline plasma levels using a regression-based path model. Lastly, we will also examine if the frequency of cardiovascular side effects is different between treatment arms while considering if participants are currently taking HAART or not by including a covariate for current HAART use in the logistic regression models of side effects.*

**Aim 3: Assess changes in affect and cognitive impairment as mediators of varenicline therapy's effect on quit rates.** We will use a regression-based path model approach to examine mediation of treatment effects based on MacKinnon et al. (2007). All variables will be standardized for the analyses. Candidate mediators include positive and negative affect and two cognitive performance task measures. Suspected mediators will be entered as standardized pre-post differences, continuously distributed and treated as normal in linear regression. The effects of treatment arm on mediators, and of mediators on outcome, will be assessed using linear regression and standardized variables. We will focus on changes in

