**6. Risk/Benefit Assessment**

There is minimal risk for serious adverse events. The treatments and procedures used in this study have been shown to be relatively safe. Varenicline has also been studied in several clinical trials and shown to be safe and efficacious. Nevertheless, there are risks in participating in this trial, which are described above.

However, the risks of participating in this trial are offset by the potential benefits for participants and society. Participants who enroll in this trial will benefit from the knowledge that they are contributing in an important way to potentially furthering scientific knowledge concerning ways to improve treatment for smokers with HIV/AIDS. All smokers will receive behavioral counseling for smoking cessation. Half of the sample will receive varenicline. The trial results may support the use of varenicline for the treatment of nicotine dependence among those with HIV/AIDS, thereby reducing tobacco-related morbidity and mortality in this population.

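### Completers-only and death-excluded analyses written for the smoking outcome also reach the Aim 2 severe-side-effect non-inferiority test, which has no rule for early leavers; harm-related loss heavier on varenicline would favour non-inferiority

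*Combined protocol and SAP*

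**What the plan says.** Statistical Analysis, Data Analysis, names intent-to-treat as the primary method for the study aims and adds: "we will conduct a completers only analysis of study aims and examine study aims with participants lost to follow-up due to death excluded". No aim is exempted.

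For the Aim 2 side-effect comparison, the same section specifies logistic regression and a test of whether the odds ratio lies outside a prescribed range: "we will test against the lower boundary on percent reporting only mild-moderate (i.e., < severe) side effects". It does not say how a participant with incomplete side-effect reports is classified, or what a completer is for this outcome.

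The whole-outcome missing-data rule, in Accrual, Abstinence and the Missing Data paragraph, is that a participant without smoking data is a smoker. The Missing Data paragraph justifies the completers-only analysis by noting that this rule can shrink the difference in quit rates. Otherwise the plan covers only missing questionnaire items and covariates associated with missingness.

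On timing, the Power section opens Aim 2 with comparisons at weeks 12 and 24, then states the power for this test "in terms of the frequency of severe side effects over the course of the 12-week treatment". The Side Effects section collects reports "at all time-points after the Intake Session over the course of the 24-week study, before and after medication initiation". The Power section also says that the sample of 310 is required for the Aim 2 non-inferiority analyses.

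**The concern.** For the smoking outcome, a missing participant is scored as a failure, which is a severe rule for the drug, and a completers-only analysis is a natural companion to it. A safety non-inferiority test works the other way. Losing or diluting events makes the arms look alike, and looking alike is the favourable result. The plan expects up to 20% withdrawal and provides for stopping the drug because of side effects, so loss related to side effects is foreseeable.

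A completers-only set can then remove affected participants, and a death-excluded set removes the gravest outcome from a safety comparison. In the primary analysis, a participant who leaves with nothing severe on record has no defined status. One available reading of an endpoint based on what participants report is that such a person counts as not severe. At stake is a statement that varenicline causes no important excess of severe side effects in this population, resting partly on who left.

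**Working it through.** **Inputs**
- 310 participants: "We have 80% power to detect a mean difference of 7.8 at any time-point between the treatment arms with the proposed sample of 310". Allocation: "Half of the sample will receive varenicline". Hence 155 per arm.
- Test level: "Power calculations were all approximated as t- or z-tests (2-sided" at 0.05), taken as one-sided 0.025 for non-inferiority.
- Benchmark: "61% of participants on varenicline reported no severe side effects, vs. 76% of participants on placebo, a 15% difference". Severe rates are therefore 39% and 24%.
- Assumption: the plan gives no numerical margin, so the 15-point gap is taken as the limit. As an odds ratio for a severe effect it is (0.39/0.61)/(0.24/0.76) = 2.02, with logarithm L = 0.7054.
- Assumption: all loss scenarios below. The documents give no dropout by arm or by side-effect status.

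**The plan's own figure.** Take a common rate free of severe effects of 68.5%, the midpoint of 61% and 76% (assumed), and no true difference.
- Difference scale: SE = √(2 × 0.685 × 0.315/155) = 0.0528; power = Φ(0.15/0.0528 − 1.96) = 81.1%.
- Odds-ratio scale: SE = √(2/(155 × 0.685 × 0.315)) = 0.2445; power = Φ(0.7054/0.2445 − 1.96) = 82.2%.

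The stated 80% is reproduced, with no allowance for dropout.

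**False non-inferiority with the truth at the limit.** With observed severe rates p_v and p_c and numbers analysed n_v and n_c:

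SE = √[1/(n_v p_v(1−p_v)) + 1/(n_c p_c(1−p_c))]

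P(non-inferiority) = Φ[(L − ln OR)/SE − 1.96]

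With no loss this is Φ(−1.96) = 2.5%.

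*Leavers unreported and scored as not severe.* A fraction d of each arm leaves, so each observed rate is the true rate × (1−d), with 155 per arm.

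| Loss, varenicline/placebo | p_v, p_c | OR | SE | False rate |
|---|---|---|---|---|
| 20%/20% | 0.312, 0.192 | 1.91 | 0.268 | 4.1% |
| 20%/10% | 0.312, 0.216 | 1.65 | 0.261 | 12.2% |
| 10%/20% | 0.351, 0.192 | 2.28 | 0.264 | 0.8% |

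Example, second row: ln 1.646 = 0.498; (0.7054 − 0.498)/0.261 − 1.96 = −1.17; Φ = 12.2%.

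*Completers-only.* A fraction of severe cases leaves, and 10% of the others.

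| Severe cases leaving, varenicline/placebo | p_v, p_c | n_v, n_c | OR | SE | False rate |
|---|---|---|---|---|---|
| 33%/33% | 0.322, 0.190 | 125.6, 130.9 | 2.02 | 0.293 | 2.5% |
| 40%/20% | 0.299, 0.219 | 121.4, 135.8 | 1.52 | 0.287 | 16.9% |
| 20%/40% | 0.362, 0.174 | 133.5, 128.3 | 2.70 | 0.294 | 0.2% |

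Example, second row: varenicline keeps 0.39 × 0.6 = 0.234 severe and 0.61 × 0.9 = 0.549 others, so p_v = 0.234/0.783 = 0.299. Overall loss is 22% and 12%, about 17% across the trial. In the first row the odds in both arms are multiplied by the same 0.67/0.90, so the odds ratio does not move.

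**Risk-difference scale, for comparison.** The unreported scenarios give 8.9%, 19.1% and 1.6%; the first two completers-only rows give 5.2% and 25.0%. The plan specifies an odds ratio, so the tables above govern.

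**Deaths.** At the 1.3 per 100 person-years cited in Background, 310 × 24/52 × 0.013 = 1.9 deaths are expected in 24 weeks, and 0.9 in 12. Removing two varenicline deaths, both severe cases, gives (60.45 − 2)/153 = 38.2% against 24%. That is 14.2 points, an odds ratio of 1.96 and a false rate of 3.4%.

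**The case against.** A reader might infer that the plan counts early withdrawals as free of severe effects. It does not say so. Such a person might be scored not severe, treated as missing, or classified on reports already made. A severe effect reported before leaving still counts under the primary intent-to-treat analysis.

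A reader might also infer that all the analyses lean towards calling varenicline safe. That is not general. Completers-only is unbiased on the odds-ratio scale when outcome-dependent loss is equal in the two arms, and heavier placebo loss makes the test conservative. Nothing in the documents says which arm will lose more.

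Other points reduce the likely size:
- The 20% withdrawal figure is a ceiling for the whole trial, not a forecast of people leaving unreported within 12 weeks.
- Side effects are taken at every visit after Intake, missed visits may be done by telephone, and adverse events can be reported at any hour.
- Stopping the drug need not mean leaving the study.
- Completers-only and death-excluded analyses are supplementary, and serious adverse events are reported regardless.
- The power statement does name the 12-week window, so timing needs clarification only.

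All of this stands and limits the concern. It does not supply a rule for incomplete side-effect follow-up, and it does not take Aim 2 out of the two supplementary sets. Neither set could reveal dropout driven by harm.

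**Conclusion.** The concern holds in conditional form. The plan extends two analysis sets suited to smoking outcomes to a safety non-inferiority test and leaves early leavers unclassified. Equal loss does little harm on the planned scale in the scenarios examined. Material inflation needs loss that is heavier on varenicline: about 12% with 20% against 10% unreported and scored not severe, or about 17% in completers with 40% against 20% of severe cases leaving. The death exclusion is wrong in principle for a safety comparison but small in effect.

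These sizes rest on 155 per arm, a limit inferred from the 61% and 76% benchmark, a truth exactly at that limit, and loss patterns that the documents do not give. They show what the wording permits, not what will happen. The change is worth making because it costs little and because the plan says this test requires the full sample.

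**What to change.** 1. Limit the completers-only and death-excluded analyses to the smoking outcomes.
2. For the Aim 2 side-effect test, analyse everyone who took at least one dose, as randomised. Count any severe side effect reported from first dose to Week 12, and count death in that window as an event. Report Weeks 18 and 24 separately.
3. Add a sensitivity analysis that also counts withdrawal, or stopping of study drug, attributed to a side effect.
4. For participants lost without a stated reason, add a tipping-point analysis over both arms. A worst case applied to varenicline alone is too blunt. With equal true severe rates of 31.5% and 20% varenicline loss scored severe, p_v = 0.315 × 0.8 + 0.2 = 0.452, OR = 1.79 and SE = 0.237. Non-inferiority would then be concluded only Φ((0.7054 − 0.584)/0.237 − 1.96) = 7% of the time, against 82% with no loss.

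The cost is analysis wording, a little more analysis, and a somewhat higher, less favourable event rate. Keeping the wider composite as a sensitivity analysis lets the 61% and 76% benchmark and the stated 80% power still apply to the main test. Table 2 lists no reason-for-withdrawal item, so confirm that the reason can be taken from the adverse-event and study-physician records.

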## OBJECTIVES

### 1. Overall Objectives

**Aim 1: Compare 12-weeks of varenicline treatment and behavioral counseling to 12-weeks of placebo treatment and behavioral counseling for treating nicotine dependence among individuals with HIV/AIDS.** Hypothesis: Varenicline and counseling will significantly increase end-of-treatment (week 12) and 24-week biochemically-confirmed 7-day point prevalence abstinence, vs. placebo and counseling.

**Aim 2: Assess effects of varenicline therapy on quality of life (QOL) and varenicline-associated side effects.** Hypothesis: QOL will be rated higher in the varenicline and counseling group vs. the placebo and counseling group, and there will be no significant differences between treatment arms in terms of the frequency of severe varenicline-related side effects.

**Aim 3: Assess changes in affect and cognitive performance as mediators of varenicline therapy's effect on quit rates.** Hypothesis: Improved affect and reduced cognitive impairment will mediate the effect of varenicline therapy on quit rates.

**Exploratory Aim: Explore participant-related variables as moderators of varenicline therapy's effect on quit rates.** To generate new hypotheses, we will explore participant-related variables as moderators of varenicline therapy's effect on quit rates, including socio-demographic (e.g., gender, race), psychiatric (e.g., depression), and medical (e.g., HIV/AIDS symptoms, method of HIV transmission) variables. Variables were selected for this analysis based on their relationship with smoking behavior (e.g., Webb et al., 2007).

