**Aim 1: Compare 12-weeks of varenicline treatment and behavioral counseling to 12-weeks of placebo treatment and behavioral counseling for treating nicotine dependence among individuals with HIV/AIDS.** We will analyze quit rates using mixed effects logistic regression. The model will include a term for time-point and, possibly, a *small number of covariates as needed*. The hypothesized effect of treatment arm (placebo vs. varenicline) will be tested by including a dichotomous term for treatment arm; we will also test for an interaction between time-point and treatment. Outcomes of the logistic regression analyses will be characterized by odds ratios (e.g., odds of quitting smoking) and 95% confidence intervals. Although quit-rates at the end of 12 and 24 weeks will represent our primary outcome variables, similar logistic regression analyses will be performed for other measures of quit rates, including prolonged and continuous abstinence. In addition, many participants will fail to become completely abstinent, but may show a reduction in smoking. A secondary analysis will examine the effect of treatment arm on daily cigarette counts using mixed effects negative-binomial regression. Likewise, time to (recurrent) event models will be fitted using Cox regression, stratified by event sequence, as in [name] et al. (2010b), to assess lapse and recovery events over 24 weeks.

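### Aim 1 claims an effect at week 12 and at week 24, but the plan tests it with one treatment-arm term, names no week-specific contrast, and attaches no action to the interaction test

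*Combined protocol and SAP*

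**What the plan says.** The Aim 1 hypothesis (Objectives, Overall Objectives) names two time-points: "Varenicline and counseling will significantly increase end-of-treatment (week 12) and 24-week biochemically-confirmed 7-day point prevalence abstinence". The Power section agrees: "The primary analysis is a comparison in week 12 and 24 cotinine-confirmed 7-day point prevalence quit rates between placebo and varenicline". It then powers each week from its own pair of proportions.

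Under Data Analysis, Aim 1, the method is "We will analyze quit rates using mixed effects logistic regression". On the model's content it says "The model will include a term for time-point", with a few covariates possible. On the test it says "The hypothesized effect of treatment arm (placebo vs. varenicline) will be tested by including a dichotomous term for treatment arm", and the same sentence goes on: "we will also test for an interaction between time-point and treatment". On reporting it says "Outcomes of the logistic regression analyses will be characterized by odds ratios (e.g., odds of quitting smoking) and 95% confidence intervals". The section then confirms that the quit rates at 12 and 24 weeks are the primary outcome variables.

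The section does not give:
- an arm contrast at week 12 or at week 24;
- any consequence of a significant or non-significant interaction;
- whether one or both weeks must succeed, or how alpha is shared;
- the random-effect structure;
- whether week 18 enters the primary model;
- whether the odds ratio is conditional or population-averaged.

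Drugs or Devices, Dosing, ends study medication at Day 84. Week 12 is therefore the end of treatment, and week 24 is about 12 weeks later.

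**The concern.** A single arm term in a model with arm and time assumes the same log odds ratio at each modelled week. There is reason to doubt that here, because one assessment is at the end of treatment and the other is well after it. The plan's own expected difference falls from 29.1 to 19.0 points.

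Two errors become possible. A common term driven by week 12 may be read as support for the 24-week claim. Or an absent week-24 effect may pull the common term down and hide a real end-of-treatment effect.

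The interaction test does not settle this as written:
- If it is non-significant, the common term presumably speaks for both weeks.
- If it is significant, no contrast is specified to replace the common term.
- If the interaction stays in the model, the arm term becomes the effect at whichever week is coded as the reference, which the plan does not state.

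The choice among these would be made with the results in view.

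**Working it through.** **Inputs from the documents.** N = 310; half receive varenicline, so 155 per arm; two-sided alpha 0.05; missing outcomes counted as smoking, so all 310 stay in. Week 12: 21.2% vs 50.3%. Week 24: 14.5% vs 33.5%.

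**Assumed.** Within-person correlation between the weeks of about 0.36 to 0.59, and a random-intercept SD of 1 to 4. The documents give neither.

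**Step 1: the plan's own power.** For a two-proportion z-test, power = Φ{[d − z·√(2p̄(1−p̄)/n)] / √[(p₁(1−p₁)+p₂(1−p₂))/n]}, with n = 155 and z = 1.96.
- Week 12: p̄ = 0.3575. (0.291 − 1.96×0.0544)/0.0519 = 3.55, power 99.98%. The stated figure of over 90% reproduces.
- Week 12, 15 points (21.2% vs 36.2%): (0.150 − 1.96×0.0514)/0.0507 = 0.97, power 83.5%, or 80.1% with continuity correction. The stated 80% reproduces.
- Week 24: p̄ = 0.24. (0.190 − 1.96×0.0485)/0.0473 = 2.01, power 97.8%. The stated 85% does not reproduce. It understates power, and nothing below depends on it.

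These are week-specific calculations. None of them is the power of a common arm term.

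**Step 2: the common term, by simulation.** I generated correlated binary outcomes at the two weeks and fitted a random-intercept logistic model with time and arm. Arm and interaction were tested by likelihood ratio, and each week by a z-test. The starting placebo rates were 21.2% and 14.5%.

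| True effect, week 12 / week 24 | Arm term significant | Weekly contrast significant | Arm significant, but interaction and week 24 both not |
|---|---|---|---|
| 29.1 / 19.0 points (planned) | 100% | week 24: about 98% | 0–2% |
| 15 / 0 points | 50–58% | week 12: 80–85% | 8–12% |
| 15 / 5 points | – | week 24: 21–28% | about 30% |

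The last column is the least precise. With 200 trials per scenario the standard error of a 10% share is √(0.1×0.9/200) = 2.1 points, and of a 30% share 3.2 points. Reruns with 400 to 600 trials, using two ways of generating the correlation, gave 4–18% for the 15/0 row and 23–37% for the 15/5 row. Read these entries as about one in ten and about three in ten.

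**Step 3: the scale of the odds ratio.** The population ORs implied by the planned rates are (0.503/0.497)/(0.212/0.788) = 3.76 and (0.335/0.665)/(0.145/0.855) = 2.97. In a random-intercept model, each arm's intercept η solves ∫expit(η+σu)φ(u)du = p, and the conditional OR is exp(η_var − η_plc).

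| σ (assumed) | Week 12 | Week 24 |
|---|---|---|
| 1 | 4.85 | 3.55 |
| 2 | 8.46 | 5.40 |
| 3 | 16.58 | 9.08 |
| 4 | 34.24 | 15.97 |

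The same quit rates therefore give very different odds ratios, depending on a variance the plan does not mention.

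**Step 4: power with weekly contrasts.**
- Both weeks required, each at 0.05: power at the planned rates is at least 0.9998 + 0.9776 − 1 = 97.7%.
- Either week sufficient, each at 0.025 (z = 2.241): 99.9% at week 12 and 95.7% at week 24.
- For a 15-point difference, the split lowers power from 83.5% to 75.4% at week 12 and from 89.4% to 83.2% at week 24.

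**The case against.** The strongest reply is that the plan does look for a difference between weeks, because the sentence naming the arm term also commits to the interaction test. The text calls both weeks primary and powers both, so week-specific reporting may well be intended. If the interaction is in the model, the arm term is not a pooled effect at all. This stands in part. A reader might infer that the plan definitely pools the two weeks and so cannot answer its own hypotheses; the documents do not support that. They leave the contrast that carries the claim undefined.

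A second reply is that the waning scenarios are not the protocol's. That stands. At the planned rates the arm term would mislead about week 24 in 0–2% of trials, so the documents give no ground for calling a false 24-week claim likely. The 15/5 case also involves a real, small week-24 effect. What goes wrong there is a claim that week 24's own test usually fails to support, not a claim about an effect that does not exist.

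Third, a subject-specific odds ratio is a valid estimand, and the plan never says its odds ratio is a population one. That stands too, so this limb is about labelling and not about the validity of the test.

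None of these replies supplies the missing contrast or says what the interaction result would change.

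**Conclusion.** The point holds in limited form. The Aim 1 test as written does not match the two week-specific claims it is meant to support, and testing the interaction without a rule does not repair this. The consequence is negligible if the planned rates are right. If the effect wanes fully by week 24 from 15 points at week 12, power falls by roughly 25 to 30 points compared with a week-12 contrast, and about one trial in ten gives a significant arm term with no warning from either the interaction or the week-24 contrast. If it wanes to 5 points, about three in ten do.

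These sizes rest on the assumed correlation and on a random-intercept model that the plan does not spell out. The sample size is adequate for weekly contrasts at the planned rates, so the issue is what can be concluded, not how many to enrol. The odds-ratio scale is a secondary reporting matter.

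**What to change.** Amend Data Analysis, Aim 1, as follows.

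1. Keep arm, time and arm-by-time in the primary model, state the random-effect structure, and say whether week 18 is included.
2. Make the week-12 and week-24 arm contrasts the primary tests, whatever the interaction p-value. Report the interaction as description only.
3. State the success rule. If both weeks must succeed, test each at 0.05. If either suffices, split alpha (for example 0.025 each) or test in a fixed order; without this, two tests at 0.05 allow a type I error of up to 0.05 + 0.05 = 0.10.
4. Label the mixed-model odds ratio as subject-specific. Beside it, report for each week the risk difference or population-averaged odds ratio with 95% CI, from GEE or by standardising the fitted model.

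No new data or visits are needed. The cost is a few lines of analysis text and, if alpha is split, somewhat lower power per week: about 2 points at week 24 at the planned rates, and 6 to 8 points for a 15-point difference.
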